### **2. Study Design**

Include an explanation of the study design (e.g., randomized placebo-controlled, cross-over, cross-sectional, longitudinal, etc.) and, if appropriate, describe stratification/ randomization/blinding scheme.

This is a longitudinal study with matched prospective controls. The patients will undergo treatment and follow-up over the course of 1-7 months. Their results will be compared to that of matched prospective controls with similar treatment and follow duration. There is no placebo, and patients will not be blinded.

Patients will be stratified based on their lesion type and the size of the lesion as these factors may impact the response to laser treatment and thus the data measurements from OCT. Photographs of the patients' treated lesions will be rated for lesion improvement by blinded physicians. OCT measurements of the lesion of interest will be used to validate the improvement and cosmetic results.

Provide precise definitions of the study endpoints and criteria for evaluation; if the primary outcomes are derived from several measurements (i.e., composite variables) or if endpoints are based composite variables, then describe precisely how the composite variables are derived.

Primary endpoints include photographic improvement of the lesion(s) of interest after 1 or more laser treatments. Two board certified dermatologists grade the degree of improvement (clearance of the lesion) in quartiles (no clearance=0-25, mild clearance=26-50, good clearance=51-75, excellent clearance=76-95, complete clearance=96-100). It will be up to the experienced treating dermatologist to determine the number of treatments necessary for maximum clearance of the lesion(s).

Secondary endpoints include measurements with OCT, which show reduced lesion thickness, lesion size, size of blood vessels, and density of blood vessels, and number of superficial blood vessels.

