Some subjects may be asked to participate in more than one imaging session. They will have the option of refusing participation in additional sessions. Follow-up examinations will be performed every 4 weeks. During these examinations, photography and imaging of the lesion of interest will be performed with optional laser treatments to be performed at the discretion of the treating physician and the patient. If no laser treatment is necessary, then the visit should take no more than 30 minutes for a quick follow-up and imaging. Additional laser treatment will require no more than 30 minutes to complete. The number of follow-ups is also determined at the discretion of the treating physician and the patient but could range from 1 to 6 depending on the response of the lesion to treatment.

Matched prospective controls will be gathered to be compared against the imaged, treated, experimental group. The prospective controls will be matched to age, gender, skin type, and type of skin lesion. They will be gathered via a retrospective chart review by abstracting and data directly from our own records.

Describe the duration of a subject's participation in the study. If there are sub-studies, include duration of participation in each sub-study.

For each visit: history and skin examination-30 minutes, imaging – up to 30 mins, and laser treatment – up to 30 mins. These are all maximums and will likely be shorter.

At a follow-up, the patient may or may not receive a laser treatment thus shortening the visit. A patient would be expected to have 1-6 follow ups depending on their response to treatment, so their maximum time in this study could range from about 1 to 6 months. Each follow-up visit is made about 4 weeks from the prior visit.

List data collection instruments (e.g., measures, questionnaires, interview questions, observational tool, etc.).

*Investigator-authored, non-standardized, or un-validated measures must be submitted for review.*

Standardized photography,  
OCT

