##### Statistical Analysis Plan

Primary Objective: The outcome of degree of improvement will be compared between those previous patients that were treated conventionally as a prospective control and those prospective patients who will be treated with assistance from the OCT device. We will use a two-sample t-test to examine the difference in degree of improvement between the two groups at each treatment.

Secondary Objective: We will present the mean/standard deviation and 95% confidence interval of all secondary outcomes (including lesion thickness, size, size of blood vessels, and density of blood vessels, and number of superficial blood vessels.) at each treatment.

2. Describe the primary statistical method(s) that will be used to analyze the primary outcome(s) or endpoints.

N/A

3. Describe the secondary statistical method(s) that will be used to analyze the secondary outcome(s) or endpoints.

N/A

4. If appropriate describe secondary or post hoc analyses of primary outcome(s) or other exploratory analysis.

N/A

5. Sample Size Determination: Explain how the overall target sample size was determined (e.g., power analysis; precision estimation), providing justification of the effect size for the primary outcome based on preliminary data, current knowledge/literature and/or cost consideration; if appropriate, provide sample size justification for secondary outcomes. Power analysis should (at least) match the primary outcome/endpoint.

Literature indicated that laser treatment of skin lesions yields varying degree of clearance across different types of lesions. For example, the Ashinoff et al. 1991 study showed 50% lesion clearance after 3 laser treatments for port wine birthmarks in 12 infants. Another Ashinoff et al. 1991 study showed 70% lesion clearance after 3 laser treatments for capillary hemangiomas in 10 infants. The Clark et al. 2002 study showed 50% lesion clearance after 3 laser treatments for rosacea in 12 adults. Last but not least, the Geronemus 1991 study showed 90% lesion clearance after 1 laser treatment for spider telangiectases in 12 adults. Based on these data, we calculated a mean of 65% ( $\pm 20\%$ ) lesion clearance after 3 laser treatments for any lesion type. Adjusting for the unique characteristics of our patient population at UCI, we estimated a mean lesion clearance of 40% ( $\pm 20\%$ ) after 1 laser treatment for any lesion type.

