The two studies of laser treatment with OCT imaging assistance, Weibel et al. 2016 and Weibel et al. 2018, demonstrated that the depth of lesions and the size and density of the surrounding blood vessels varied widely across patients with burn and traumatic scars and vascular hemangiomas, and that some lesions appearing to be superficial had a much deeper component than could be visualized or palpated. Based on this insight, we hypothesized that laser treatment with imaging assistance would enable dermatologists to calibrate the laser parameters precisely to the actual depth of a lesion and the actual size and density of the surrounding blood vessels; as a result, at least 60% ( $\pm 20\%$ ) of the lesion of any type would be cleared after one laser treatment with imaging assistance as compared to 40% ( $\pm 20\%$ ) without imaging assistance.

A sample size of 34 patients, including 17 patients prospectively treated with laser and imaging assistance for lesions of any type and 17 prospective controls who received laser treatment without imaging assistance, would yield 80% power to test the aforementioned hypothesis using a two-sided two-sample t test at 5% significance level.

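### Controls are matched on four factors and patients stratified on two, but the primary two-sample t-test uses neither; if matched outcomes correlate positively, the test is conservative and its interval too wide

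*Combined protocol and SAP*

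**What the plan says.** Section 6, Study Design, describes the design in one line: "This is a longitudinal study with matched prospective controls". Section 6, Research Procedures, names the matching factors: "The prospective controls will be matched to age, gender, skin type, and type of skin lesion". Neither section gives a ratio, an age tolerance, a selection rule or any mention of pairs or sets.

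Study Design adds a second structure: "Patients will be stratified based on their lesion type and the size of the lesion as these factors may impact the response to laser treatment". The documents do not say where this stratification is applied.

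The Primary Objective in the Statistical Analysis Plan then reads: "We will use a two-sample t-test to examine the difference in degree of improvement between the two groups at each treatment". The later items of that section that ask for primary, secondary and exploratory methods are answered as not applicable, so no other analysis takes up the matching or the strata.

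The sample size paragraph rests on the same test. It plans 34 patients, "including 17 patients prospectively treated with laser and imaging assistance for lesions of any type and 17 prospective controls who received laser treatment", and says that this number "would yield 80% power to test the aforementioned hypothesis using a two-sided two-sample t test at 5% significance level". The assumed mean clearances are 60% with imaging and 40% without, each with a plus/minus figure of 20 points. The enrolment table in Section 3 repeats 17 per group, with a maximum of 30 per group.

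**The concern.** Matching on a factor that predicts the outcome makes the two groups more alike than two independent samples would be. The true variance of the difference in means is then smaller. A two-sample t-test still computes its standard error as if the groups were independent, so the variation that matching has removed from the comparison stays in the error term.

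The plan gives reason to expect such a factor. Its sample size section says that clearance varies across lesion types and cites 50%, 70%, 50% and 90% for four of them. Study Design says that lesion type and size may affect response. Lesion type is both a matching factor and a stratification factor.

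The error is in the conservative direction: it does not raise the false-positive risk. It gives a wider interval than the design supports and makes a real benefit somewhat easier to miss. In a 34-patient pilot, the interval is one of the main results on which a later study would be planned.

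**Working it through.** **Inputs.** From the sample size section: difference 60 − 40 = 20 points, SD 20 in each group (reading the plus/minus figure as an SD), 17 per group, two-sided 5%. The correlation ρ between matched patients' outcomes is not in the documents; it is an assumption, shown for 0 to 0.5. Clearance is treated as a normally distributed percentage.

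**Step 1: the plan's own figure.** Unpaired standard error = 20 × √(2/17) = 6.86. Noncentrality = 20 / 6.86 = 2.92 on 32 degrees of freedom. The noncentral t distribution gives power of 80.7% at 17 per group and 78.1% at 16. The stated 17 per group reproduces.

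**Step 2: matching in 1:1 pairs.** True standard error = 20 × √(2(1 − ρ)/17), so the unpaired one is too large by 1/√(1 − ρ). The 95% half-width is 2.037 × 6.86 = 14.0 points unpaired (32 df), and 2.120 × the true standard error paired (16 df). Paired power is from the noncentral t. The unpaired test's real type I error and power come from simulating 17 correlated pairs (1,000,000 trials per value of ρ).

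| ρ (assumed) | True SE | SE too large by | Unpaired: real type I error | Unpaired: power | Paired: power | Paired: half-width |
|---|---|---|---|---|---|---|
| 0 | 6.86 | 1.00 | 5.0% | 80.7% | 78.1% | 14.5 |
| 0.2 | 6.14 | 1.12 | 3.0% | 83.2% | 86.4% | 13.0 |
| 0.3 | 5.74 | 1.20 | 2.1% | 84.7% | 90.5% | 12.2 |
| 0.5 | 4.85 | 1.41 | 0.8% | 88.1% | 97.2% | 10.3 |

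The power forgone is about 3, 6 and 9 points at ρ of 0.2, 0.3 and 0.5. The paired test has higher power once ρ exceeds 0.063. Its interval is narrower once ρ exceeds 1 − (2.037/2.120)² = 0.077.

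**Step 3: matching by group.** If only the mix of lesion types is balanced, there are no pairs. I simulated four types with 5, 4, 4 and 4 patients in each group, total SD 20, and compared the planned test with a linear model of study group plus lesion type (34 − 5 = 29 df; 200,000 trials per setting). The type means follow the pattern of the four cited clearances, rescaled so that type explains the stated share of variance.

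| Variance explained by type (assumed) | Unadjusted: type I error | Unadjusted: power | Adjusted: power |
|---|---|---|---|
| 0% | 5.0% | 81% | 80% |
| 20% | 2.9% | 83% | 88% |
| 30% | 1.9% | 84% | 92% |
| 50% | 0.5% | 88% | 98% |

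The adjusted model holds 5% throughout. If the type means are instead drawn at random, unadjusted power at 30% is 86% rather than 84%, and the adjusted figure stays at 92%. If type explains nothing, adjustment costs about 0.3 points (80.4% against 80.7%). Both forms of matching therefore lead to the same conclusion.

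**The case against.** Four points can be made for the plan as it stands.

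**The documents never say that matching is individual.** A reader might infer 1:1 pairs from the equal numbers, 17 and 17, or 30 and 30. Those numbers fit group matching just as well. Under group matching a paired t-test is not available. This stands, so the remedy cannot be a paired test alone. It does not remove the point, because step 3 shows the same conservatism under group matching.

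**The correlation is unknown.** At ρ = 0 the planned test is exact and the paired test is worse by 80.7 − 78.1 = 2.6 points. This stands: the consequence is conditional. The four cited clearances are weak evidence on its size. They come from groups of 10 to 12 patients and mix infants with adults and one treatment with three. Their SD is 19.1, but the three figures after three treatments (50, 70, 50) have an SD of only 11.5. They support a positive correlation, not a value.

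**The planned power is met.** A reader might infer that the trial falls short of 80%. It does not. The size was calculated for the unpaired test, and that test's real power rises above 80.7% as ρ rises. A reader might also add a within-type SD of 20 to the between-type 19.1 and find much lower power. That makes the total SD √(19.1² + 20²) = 27.7, and two fully independent groups would then have only 53% power. The fall comes from the larger SD, whereas the plan applies 20 points as the total spread for lesions of any type.

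**Pairing has a practical cost.** Comparisons are made at each treatment, while further treatments are optional and follow-ups range from 1 to 6. A paired t-test drops both patients when either lacks a later treatment. This stands against the paired t-test; a mixed model keeps the remaining patient.

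**Conclusion.** The design and the primary analysis do not fit together. Controls are matched on four factors and patients stratified on two, and the planned test uses none of them. If matched patients' outcomes correlate positively, the test is conservative and its interval too wide. For assumed correlations of 0.2 to 0.5, the real type I error is 3.0% down to 0.8%, about 3 to 9 points of power are forgone, and the half-width is 14.0 points where 13.0 to 10.3 would do.

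This rests on the plan's SD of 20 and difference of 20, on 17 complete pairs (or balanced lesion types), and on a correlation that must be assumed. The documents do not support three stronger readings: that matching is known to be individual, that the loss is certain, or that the trial misses its 80% power. The analysis should be changed, because the change is cheap and the set identifier may be hard to recover once the control records have been abstracted.

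**What to change.** 1. **Research Procedures:** state whether controls are matched 1:1, in sets or by group.
2. **If 1:1 or in sets:** record a matched-set identifier when each control is selected. In the Primary Objective, replace the two-sample t-test at each treatment with a linear mixed model of clearance on study group with a random effect for matched set, using small-sample degrees of freedom. A paired t-test serves when all pairs are complete.
3. **If by group:** use a linear model of clearance on study group, adjusted for lesion type first, then for the other matching and stratification factors as far as 34 patients allow. Name the covariates in advance.
4. **Sample size paragraph:** keep 17 per group, and note that the two-sample formula ignores any gain from matching and is therefore a conservative basis.

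The cost is a few sentences and, for individual matching, one data column. The statistical price is fewer degrees of freedom: about 2.6 points of power for a paired test if the correlation is zero, and under 1 point for adjustment by lesion type if type explains nothing. A paired t-test also loses pairs with a missing partner at later treatments, which the mixed model avoids.

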### **SECTION 3: SUBJECT POPULATION(S) (INDIVIDUALS/RECORDS/SPECIMENS)**

#### **1. Subjects To Be Enrolled on this UCI protocol (Persons/Records/Biospecimens)**

1. Complete the table of subject enrollments below. *Include additional rows for subject category/group, as needed.*
2. If the study involves the use of existing records or biological specimens, specify the maximum number to be reviewed/collected and the number needed to address the research question.

Category/Group (e.g., adults, controls, parents, children)	Age Range (e.g., 7-12, 13-17, adults)	Maximum Number to be Consented or Reviewed/Collected (include withdrawals and screen failures)	Number Expected to Complete the Study or Needed to Address the Research Question
Study Group	All ages	30	17
Control group (prospective controls)	All ages	30	17
Total: 60			

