**Originally collected for research purposes:**

NO – Please explain: [<Type here>](#)

YES – UCI IRB approval granted under IRB protocol number (i.e. HS#): [<Type here>](#)

YES – Non-UCI IRB approval granted. Confirm one of the following:

A copy of the IRB Approval Notice and Consent Form for the original research collection will be submitted with the IRB application (APP). The IRB Approved Consent Form does not preclude the proposed activity.

A copy of the commercial Vendor Policy or a Letter from the Vendor attesting that the information was collected and will be shared in an appropriate and ethical manner will be submitted with the APP. The vendor's policy does not preclude the proposed activity.

5. Provide a complete list of the **data points, variables, and/or information** that will be collected **during the screening process** (i.e. data abstraction form). *Note: Only the minimum information necessary to determine subject eligibility should be collected during the screening process.*

For the experimental group, we would screen for the patient's age, type of lesion/diagnosis, location of the lesion, and the patient's willingness and ability to participate in the study.

For the control group, we would screen for the patient's age, type of lesion/diagnosis, location of the lesion, and the clearance of the lesion and response to treatment.

Check here if the list is submitted as a separate document with the application.

6. Specify what will happen to the information and/or biospecimens, if the potential subject is not eligible to participate in the study. *Note: Information or biospecimens of non-eligible subjects, may not be included as part of data analysis or disclosed beyond the study.*

The study team plans to destroy the identifiable information and/or biospecimens at the earliest opportunity consistent with conduct of the research. Describe the protocol specific plan and timeframe for destruction: [<Type here>](#)

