Once the subjects have been identified as appropriate candidates for this pilot study, the protocol will be explained in detail to the patient and/or if appropriate the parent or legal guardian at a convenient time for the patient/parents by the physician investigators. Subjects will be considered appropriate if they have a skin area of interest for imaging and laser treatment is planned. Consent form, and HIPAA authorization form will be obtained including written UCI assent forms, from eligible infants/children/minor patient consent will be obtained from the patient's parent(s) or legal guardian(s).

Subjects will be informed that their participation in the pilot study is completely voluntary, and that a decision either to participate or not will not affect their care in any way. They will be given as much time as they wish to decide on participation, and will be told that they may discontinue participation at any time. Written consent will be obtained from all populations. Consent Form for Adults and assent for Children ages 13-17, and minor assent forms (ages 4-12 years old) will be obtained. Informed consent form in the way of parental permission will be collected for minors aged 0-3 who cannot yet provide assent. Parent will only be approached about participation in study after birth of their child and not before. This can be feasibly carried out via postnatal permission without compromising study design.

1. Some subjects may be vulnerable to coercion or undue influence, such as those who are economically or educationally disadvantaged, mentally disabled, or students (undergraduate, graduate, and medical students) and employees of UCI (administrative, clerical, nursing, lab technicians, post-doctoral fellows and house staff, etc.), describe the procedures to ensure the voluntary participation of these individuals.

Not applicable: Subjects are not vulnerable to coercion or undue influence.

Other (specify): Please see above explanation regarding children and consent/assent.

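### Controls are screened on their recorded clearance while OCT patients are enrolled before any outcome exists, so unequal outcome-related selection could bias the primary t-test by an unknown amount in either direction

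*Combined protocol and SAP*

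**What the plan says.** **Primary analysis.** The Statistical Analysis Plan in Section 6 states: "We will use a two-sample t-test to examine the difference in degree of improvement between the two groups at each treatment". Items 2 to 4 of the same section, which ask for the primary, secondary and exploratory methods, are answered N/A. No section gives an analysis set, a rule for withdrawals or a rule for missing grades.

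**Outcome.** Section 6, Study Design, makes the primary endpoint a photographic grade of clearance after one or more laser treatments, rated by blinded physicians. Section 6, Research Procedures, provides photographs immediately after the first treatment and at follow-ups every 4 weeks. There are 1 to 6 follow-ups, at the discretion of physician and patient. No section says which photograph is graded.

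**How OCT patients enter.** They consent, are imaged and are treated at visit 1. Section 5, Methods of Informed Consent, tells them that "they may discontinue participation at any time". Their screening list (Section 3, Screening and Determining Eligibility, item 5) covers age, lesion type, lesion location, and willingness and ability to take part.

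**How controls enter.** Research Procedures has them gathered by retrospective chart review, and the Statistical Analysis Plan describes them as previously treated patients. For them, item 5 says "we would screen for the patient's age, type of lesion/diagnosis, location of the lesion, and the clearance of the lesion and response to treatment". Yet the enrolment table, Study Design and the sample-size text call the controls prospective.

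**Numbers.** The enrolment table allows each group a maximum of 30, a count that is to "include withdrawals and screen failures". Against this it sets 17 per group under "Number Expected to Complete the Study or Needed to Address the Research Question".

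**The concern.** The two groups reach the t-test by different routes. An OCT patient is committed to the study before anyone knows how the lesion will respond. If no usable later photograph exists, that patient can silently leave the analysis. A control candidate is considered with the result already on the chart and listed as a screening item. A conventionally treated patient with no recorded result can be passed over without being counted, and nothing prevents a choice that leans on how good the result was.

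Returning for follow-up may well depend on the result. If poor responders are missing more often from the OCT group than from the controls, the comparison favours OCT with no true effect. If good responders are the ones missing, a real effect shrinks. The t-test and its 5% level allow for neither. With no analysis set and no count of ungraded patients in either group, a reader of the results could not tell which had happened.

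**Working it through.** **1. The plan's own figure.** Inputs from the sample-size text: clearance of 60% against 40% after one treatment (difference 20 points), ±20% read as the SD (an assumption), 17 per group, two-sided 5% t-test. The standard error is 20 × √(2/17) = 6.86, so the noncentrality is 20/6.86 = 2.92 on 32 df. The exact power is 80.7%, and the exact requirement for 80% is 16.71, rounded up to 17 per group. The statement that this size "would yield 80% power to test the aforementioned hypothesis using a two-sided two-sample t test at 5% significance level" reproduces. The planned size is not in dispute.

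**2. General form of the bias.** In one group let d be the fraction treated but not graded, and g the mean of the graded minus the mean of the ungraded. The mean of all treated patients is (1 − d) × graded + d × ungraded, so the graded mean exceeds it by d × g. The bias in the difference is therefore

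bias = d(OCT) × g(OCT) − d(control) × g(control).

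It is zero when the two products are equal. Choosing controls on the size of their recorded result acts like a further term in the control product.

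**3. Selection in the OCT group only (assumed).** Set the control product to zero and take 17 graded per group with SD 20. The documents give no loss rate and no outcome gap, so both are shown as ranges. The sign follows the sign of g.

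| OCT loss d | Gap g (points) | Bias d × g (points) | Two-sided type I error |
|---|---|---|---|
| 10% | 10 to 20 | 1 to 2 | 5.2% to 5.9% |
| 20% | 10 to 20 | 2 to 4 | 5.9% to 8.7% |
| 30% | 10 to 20 | 3 to 6 | 7.1% to 13.6% |
| 43% (13/30) | 10 to 20 | 4.3 to 8.7 | 9.4% to 23.2% |

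**4. Simulation of the same case.** OCT clearance is drawn from a normal distribution with SD 20, and 17 patients are kept. Those on one side of the group mean are two or three times as likely to be kept. The 17 controls are drawn unselected with mean 40, and a pooled t-test is used.

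- No true effect, better responders kept, 17 of 30: false difference about +3.4 points (twofold) or +5.3 points (threefold). The chance of a significant result for OCT is about 7% or 12%, against a nominal 2.5%.
- True gain of 20 points, poorer responders kept, 17 of 30: the estimate falls to about 16.5 or 14.7 points, and power to about 65% or 56%.
- Milder loss, 17 of 21, twofold: +1.9 points with no true effect. With a true gain of 20 and the opposite selection, power is about 73%.

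**5. The same selection in both groups.** With the twofold or threefold rule applied to controls as well, the false difference is about 0 and the chance of a significant result for OCT is about 2.5%. With a true gain of 20 points the estimate is about 20 and power is 82% to 84%. All the bias in steps 3 and 4 comes from the assumed asymmetry.

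**The case against.** Four counter-arguments have weight.

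**Every treated OCT patient has a post-treatment photograph.** A reader might infer that a patient who does not return has no score. Research Procedures does not support that: photographs are taken immediately after the first treatment, expressly to assess its results. What is missing is a statement of which photograph is graded. That gap still matters, because returners could be graded at 4 weeks and non-returners on the day of treatment.

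**Controls with a recorded outcome are completers too.** A reader might infer that losses fall on the OCT group alone. They need not. Conventionally treated patients who did not return are removed when charts are selected, so the t-test may compare completers with completers. If the selection is alike, the bias cancels (step 5). This limits the point to a risk, but nothing in the plan makes the two selections alike or lets anyone check.

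**13 of 30 is not a dropout rate.** The 30 is a ceiling that includes screen failures, the 17 is the power-calculation number, and both groups have the same pair. The 43% row is an outer case only.

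**The controls may be prospective.** If they are, they can be lost in the same way and the asymmetry weakens. The documents say both things, and the screening list with clearance on it fits only the chart-review reading.

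**Conclusion.** The point stands as a risk of bias from unequal entry routes, not as a demonstrated bias. The documents themselves make recorded clearance and response a screening item for controls and not for OCT patients. They also leave the analysis set, the graded time point and ungraded patients undefined.

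Sign and size are unknown. If selection acted on the OCT group only (17 of 30 graded, SD 20, twofold to threefold), the false difference would be about 3 to 5 points against a planned effect of 20. The chance of a significant result for OCT would be about 7% to 12% instead of 2.5%. With equal selection both excesses disappear. Loss rates, outcome gaps and selection strengths are all assumptions. The documents do not support a claim that the plan necessarily favours OCT.

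**What to change.** 1. **Control selection (Section 3, screening item 5, and Section 6, Research Procedures).** Remove clearance and response from control screening. Choose controls on baseline and treatment data only, for example consecutive eligible treated patients who meet the matching factors. Keep the outcome masked, and select whether or not a later photograph exists.
2. **Analysis set (Statistical Analysis Plan).** Define the primary set as all patients in both groups who received the first laser treatment.
3. **Graded photograph.** Name one time point, the same for both groups, so that a same-day image is not graded for some patients and a 4-week image for others.
4. **Reporting and sensitivity.** Report the number treated but ungraded in each group. Add a tipping-point analysis that varies the assumed clearance of ungraded patients until the conclusion changes. Multiple imputation can be a further sensitivity analysis. It need not be the primary method, because it assumes that observed data explain the missingness and would be unstable with so few patients and several lesion types.
5. **Consistency.** Reconcile the prospective label in the enrolment table, Study Design and the sample-size text with the chart review of previously treated patients in Research Procedures and the Statistical Analysis Plan.

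The cost is some extra chart-review and analysis work, with no added study procedures. The estimate may become somewhat less favourable or less precise than one based only on patients with a convenient grade.
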